6.2. Screen Failures

Screen failures will include any subject who was consented, but subsequently did not meet the entry criteria in order to receive study product. Subjects who fail screening will not be followed for safety or efficacy assessment, and no other study procedures will be performed. Appropriate screen failure data including reason for ineligibility will be collected on the CRF.

6.3. Study Suspension or Termination

The IRB, the Sponsor, the FDA, or other regulatory health agencies may choose to voluntarily suspend or terminate some or all activities of the study at any time if they judge that it is in the best interest of the subject. They may also suspend or terminate the study for various other reasons. They can do this without the consent of the subject.

[figure not shown]
7. STUDY PRODUCT

7.1. Product Description

Active Drug: AMG0001 (Figure 1) is a clear liquid with a pH of approximately 4.5 to 7.5 containing 2.5 mg/mL AMG0001 (plasmid construct pVAX1 HGF/MGBI) dissolved in physiological saline in a 2.10 mL volume (5.25 mg plasmid).

Name: AMG0001 may also be named “HGF” or “HGF Plasmid”

Figure 1: Schematic representation of AMG0001

7.2. Packaging and Labeling

The study product will be provided in 3 mL glass vials. Each subject package and vial is labeled to indicate the unique vial number, vial volume, date of manufacture, and the following statement “CAUTION: New Drug - for investigational use only.”

7.3. Storage

Details regarding storage of both undiluted and diluted investigational product are available in the Pharmacy Manual. Upon receipt the Investigational Product should immediately be stored in a freezer at -15°C to -25°C (5°F to -13°F). Freezers should not have an autodefrost feature and must have continuous temperature monitoring as described in the Pharmacy Manual. Once the vial is thawed at the clinical center, it should not be refrozen. Details for storage of the undiluted and diluted investigational product are available in Appendix A and the Pharmacy Manual.

7.4. Study Product Accountability

Upon receipt, the Investigator is responsible for taking an inventory of the study product. A record of this inventory must be kept and usage must be documented on study product accountability logs provided by the Sponsor. Study product accountability logs will be examined and reconciled by the study monitor.

In accordance with federal regulations (21 CFR 312.62), all Investigators are required to keep accurate records showing final disposition of all investigational drugs/study product. These records must be available to the Sponsor on request, showing accurate reconciliation of each and every shipment of study product and all activity of study product at the site (storage, dispensation to subjects, etc). The Investigator is also required to ensure adequate storage of study product, which includes appropriate documentation of such storage conditions (e.g., maintaining temperature logs, etc).

Ultimate accountability for the receipt, dispensation and record-keeping of the study product lies with the Investigator. Federal regulation requires that storage of the substance be in a secure enclosure, access to which is limited, to prevent theft or diversion. Neither the Pharmacist nor Investigator may supply the study product to any person outside of this protocol.

Dosing must be documented on the CRF for each subject in addition to the study product accountability logs.

Any unused vials must be retained at the study site until reconciliation by the study monitor. Opened (used) vials must be maintained until the study monitor confirms accountability. Once the study monitor completes accountability procedures, the used (opened) vials and any unused vials will be disposed of using each institution's recommended investigational drug and biohazard material disposition procedures.

The study product provided by the Sponsor for use in this study is intended for use only in the clinical trial outlined in this protocol and will be administered only to subjects appropriately enrolled in this trial. The use of the drug for other clinical or pre-clinical situations is strictly prohibited. AMG0001 is an investigational medication for use only in Clinical Trial AG-CLI-0209. The possession and use of AMG0001 must be closely controlled and monitored by Investigators. Upon completion of the study, the study monitor will arrange for return or destruction of all used or unused vials of study product.

8. SAFETY REPORTING

8.1. Adverse Events and Serious Adverse Events

The protocol has been designed with an understanding of the underlying cardiovascular disease and associated co-morbidities in the study population, and the unknown potential angiogenic effects of AMG0001. Although to date there are no indications that AMG0001 increases the incidence of serious nonfatal or fatal events, an evaluation of adverse events will be performed at each visit. The subject will be questioned in a non-leading manner to determine if any adverse events have occurred during product administration and during the post-treatment study period. **An event that occurs during the Screening Period (from the time informed consent to just prior to the first dose of study product administration) must be documented as part of the Medical History.**

Adverse Events should be documented and followed from the start of the first dose of study product (Day 0), until the final outcome is known or until the end of the study safety follow-up period. AEs (including SAEs) that have not resolved by the end of the study follow-up period should be recorded in the CRF as “ongoing”. If it is not possible to obtain a final outcome for a SAE, the reason that a final outcome could not be obtained must be documented (e.g., completion of follow up, subject has moved and cannot be contacted, etc.).

Each Adverse Event or Serious Adverse Events should be adequately described in the subject's medical record. The description of AEs or SAEs will include the nature of the event, the time of onset, the duration and severity of each event, the Investigator's opinion regarding the causal relationship to study product or the subject's CLI, the action taken, and the outcome of the event.

All adverse events (excluding events related to the worsening of CLI as described below) will be reported and recorded in the subjects' source documentation and the appropriate CRF.

Any **serious adverse event** (see definition below) observed by the Investigator or study staff or reported by the subject that occurs within the study period will be recorded on the appropriate CRF. These events will be reported regardless of the perceived relationship of the event to the study product.

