2. STUDY OBJECTIVES

The primary objectives of the clinical trial are:

1. To confirm the feasibility of study-related activities and the tolerability of a modified dosage regimen of AMG0001 in CLI
2. To evaluate the safety of AMG0001

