4.6. Angiogram

An aorto-iliac angiogram will be performed and will be used to determine the suitability of the subject for enrollment into the study and to determine injection site locations. The angiogram may have been completed up to 3 months prior to the start of screening, as long as the subject's clinical condition has not changed since the angiogram was performed or undergone a bypass or endovascular intervention within the previous 3 months. Acceptable forms of imaging for this trial also include Computerized Tomography Angiogram (CTA) and Magnetic Resonance Angiogram (MRA). An angiogram will also be required to be performed prior to a proposed surgical revascularization or major amputation.

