4.13. Adverse Event Review

The Investigator should start documenting adverse events after the first dose of study product administration, during study product administration, post treatment and throughout the study period (Month 18 Visit). See Section 8.0 Adverse Events for details.

Events relating to the worsening of CLI that occur in the index limb such as increased rest pain, new ischemic ulceration or increase the size of the ulcer, gangrene, cellulitis or osteomyelitis, and redness that are related to the study disease and are symptoms/signs of progression of study disease will not be recorded as adverse events (unless the speed or extent of the symptoms/signs are unexpected based on the natural history or bear a strong temporal relationship to the study product). Data on the subject's CLI status of the index limb will be recorded in detail on non-AE CRFs and is therefore not required to be documented as an AE or SAE.

In cases which any of the worsening of CLI events that occur in the index limb such as increased rest pain, new ischemic ulceration or increase in the size of the ulcer, gangrene, cellulitis or osteomyelitis, and redness that are symptoms/signs of progression of critical limb ischemia, **and that result in death**, the event should be reported as an SAE.

Systemic or metabolic complications that ensue subsequent to worsening CLI of the index leg should be reported as AEs or SAEs. Systemic complications include events such as septicemia, pneumonia, multi-organ failure and events resulting in death. These events should be captured on the AE or SAE section of the CRF. Metabolic complications include excessive increase in blood glucose or serum creatinine. Events that result in death should be reported as a SAE.

Limb specific events that occur in the **non-index limb** such as increased ischemic rest pain, new ischemic ulceration or increase in the size of the ulcer, gangrene, minor or major amputations, will be recorded as an AE or SAE on the AE CRF.

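### Serious harm from a protocol-required procedure between consent and first dose has no explicit SAE reporting route, even when that harm makes the subject a screen failure

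*Protocol*

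**What the plan says.** - **Start of collection.** Protocol 8.1 says, in bold, that an event from consent to "just prior to the first dose of study product administration) must be documented as part of the Medical History". It makes no exception for serious events or for events caused by a study procedure. The same section says "Adverse Events should be documented and followed from the start of the first dose of study product (Day 0", and 4.13 says "The Investigator should start documenting adverse events after the first dose of study product administration".
- **Screen failures.** Protocol 6.2: "Subjects who fail screening will not be followed for safety or efficacy assessment, and no other study procedures will be performed". What is kept is stated next: "Appropriate screen failure data including reason for ineligibility will be collected on the CRF".
- **Angiogram.** Protocol 4.6: "An aorto-iliac angiogram will be performed and will be used to determine the suitability of the subject for enrollment into the study". It also guides the choice of injection sites. However, "The angiogram may have been completed up to 3 months prior to the start of screening", subject to conditions on the subject's clinical course, and CT or MR angiography is accepted.
- **Debridement.** Protocol 4.9 requires it before the ulcer photographs and tracings at screening and again before dosing on Day 0. Sections 5.1 and 5.2 and Appendix D soften this to debridement where necessary.
- **Objective.** The first primary objective in Protocol section 2 begins "To confirm the feasibility of study-related activities".

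**The concern.** The interval between consent and first dose contains procedures that some subjects undergo because the protocol asks for them. Serious harm from such a procedure is not pre-existing history, and it is not a treatment-emergent event either. The plan offers only those two places for it.

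Two things are at stake. The first is patient safety: the sponsor may not learn promptly, through the SAE system, that a study procedure has injured someone, and nobody is assigned to follow that person once screening has failed. The second is the trial's own question. This is a pilot for the phase 3 study AG-CLI-0206, and serious harm from the activities being piloted bears on whether they are feasible.

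**Working it through.** The plan gives no figure on this point, so there is nothing to reproduce. The check sets the sections side by side and follows a hypothetical serious event caused by a screening procedure.

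**1. Can a required procedure fall in the interval?** Yes. Protocol 4.6 and 5.1 require an angiogram unless a recent, still valid one exists. Sections 4.9, 5.1 and 5.2 call for debridement, at least where needed, at screening and on Day 0 before dosing. Screening lasts up to 30 days.

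**2. Where is the event written down?**
- Protocol 8.1 sends it to Medical History.
- Protocol 4.13 has not yet started adverse event documentation.
- Protocol Table 2 and the list in 5.1 contain no adverse event review. The Day 0 pre-dose list in 5.3.1 has none either, whereas the pre-dose list for Days 14 to 42 in 5.5 does.
- In the SAP schedule, as far as the extracted table can be read, the Adverse Events row is blank at Screening while Concomitant Medication is marked.

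**3. Does an SAE rule pick it up?**
- Protocol 8.2.2 ties immediate reporting to receipt of investigational drug or control, to 18 months from first administration, and to the safety follow-up. Screening is not named.
- Protocol 8.1 also has a general sentence: SAEs within the study period go on the CRF and are reported whatever their perceived relation to study product. The start of that period is not defined.
- Protocol 8.2.1 has staff document adverse events that the subject discloses at baseline, which does not fit the Medical History rule.
- Causality is judged against study product or CLI (8.1), or against study product alone (8.2.5). There is no category for a study procedure.

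**4. Can the harm itself cause the screen failure?** Yes, through the protocol's own criteria:

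| Event or change during screening | Consequence |
|---|---|
| Stroke, TIA or MI | Excluded (3.3, item 13: within 3 months of entry) |
| Creatinine clearance falls below 30 mL/min, for any reason | Excluded (3.3, item 12), although 30-45 mL/min can support entry under 3.1 |
| Exposed tendon, osteomyelitis or uncontrolled infection | Excluded (3.3, item 3) |
| CLI becomes unstable | Screen failure (5.2) |

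From that point 6.2 ends safety follow-up. The remaining trace is the reason for ineligibility.

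**5. Does an analysis show it?** No. The single SAP population (2.5.1) is subjects with at least one injection, and the adverse event tables in 2.5.7 are treatment-emergent. None of the ten evaluations in Protocol 9.1 is directed at harm from screening procedures.

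**The case against.** A reader might infer from 8.1 and 6.2 that such harm is never reported, or disappears from the record. The documents do not support that:
- The Medical History rule itself requires the event to be documented.
- The study-period sentence in 8.1 and the baseline sentence in 8.2.1 can both be read to include it.
- Protocol 8.1.4 documents all deaths and gives no start date.
- Protocol 11.1 keeps the investigator's IRB/EC reporting duties.
- For a screen failure, a complication that is itself an exclusion criterion would appear as the reason for ineligibility.

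This stands as a limit on the point, but it does not close the gap. The rule on deaths covers only deaths. IRB/EC duties produce no SAE record or listing in the trial. A reason for ineligibility is not a safety report and brings no follow-up. The two general sentences contradict the specific one, and a site that obeys the bold instruction would not file an SAE.

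It is also fair to say that exposure is narrower than all consented subjects. An angiogram may predate consent, and debridement is conditional in several sections. An angiogram done before consent would lie outside the proposed rule too.

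Finally, pre-dose events say nothing about the safety of AMG0001, and the objectives do not define feasibility in terms of harm. Both statements are correct. Treating procedure harm as evidence on feasibility is a reading of the objective, though a natural one for a pilot of those procedures.

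**Conclusion.** The point holds as a gap combined with an inconsistency. No explicit rule makes a serious event caused by a protocol-required procedure before the first dose an SAE. The most specific rule points to Medical History, and follow-up stops if the subject then fails screening.

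Its size cannot be put as a rate, because the documents give no complication rate and no expected number of screen failures. A reader might reason that one event among 8-10 subjects is at least 10%. The arithmetic is 1/10 = 10% to 1/8 = 12.5%, but it applies only if the harmed subject was later dosed. For a screen failure the denominator is all consented subjects, so the share is lower and unknown. Nor can one say that the plan would report zero, since no planned table estimates this quantity.

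The treatment-emergent and efficacy summaries are unaffected. The conclusion rests on two assumptions: that some subjects have a required procedure after consent, and that sites follow the explicit sentence over the general ones. It is a cheap improvement to safety reporting and to the feasibility record, and does not threaten the planned analyses.

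**What to change.** - **Protocol 4.13, 6.2, 8.1, 8.2.1 and 8.2.2:** define when the SAE reporting period starts, and reconcile these sections with it. State that, from consent, a serious event judged caused by a protocol-required procedure is reported as an SAE and followed to outcome, including in subjects who then fail screening. Keep unrelated pre-dose events in Medical History.
- **Protocol 8.1 and 8.2.5:** add relation to study procedure to the causality assessment. Without it the new rule has no recorded judgement to work from.
- **SAP 2.5.7:** add one listing of these events, separate from the TEAEs, with consented subjects as the denominator. Identify them by a CRF item for pre-dose, procedure-related events and not by date alone, because SAP 2.4.3 treats adverse events starting on Day 0 as post-baseline.

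The cost is protocol and CRF-guideline wording, one causality item and one listing. The downside is a small reporting burden during screening.

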8.1.1. Adverse Events Associated with Worsening CLI

Adverse Events relating to the worsening of CLI that occur in the index limb such as increased rest pain, new ischemic ulceration or increase the size of the ulcer, gangrene, cellulitis or osteomyelitis, that are related to the study disease and are symptoms/signs of progression of study disease will not be recorded as adverse events (unless the speed or extent of the symptoms/signs are unexpected based on the natural history or bear a strong temporal relationship to the study product as determined by the Investigator). Data on the subject's CLI status of the index limb will be recorded in detail on non-AE CRFs and not required to be documented as an AE or SAE, unless the outcome of the event is death.

Systemic or metabolic complications (e.g., diabetic ketoacidosis, renal failure, etc.) that ensue subsequent to worsening CLI of the index leg should be reported as AEs or SAEs. SAEs due to systemic complications include events such as septicemia, pneumonia, multi-organ failure and events resulting in death. These events should be reported as an SAE.

Limb specific events that occur in the **non-index limb** such as increased rest pain, new ischemic ulceration or increase in the size of the ulcer, gangrene, minor or major amputations, will be recorded as an AE or SAE on the AE CRF

8.1.2. SAEs Associated with Worsening CLI

Serious Adverse Events relating to the worsening of CLI that occur in the index limb such as gangrene, cellulitis or osteomyelitis, are related to the study disease and are symptoms/signs of progression of study disease will not be recorded as serious adverse events (unless the speed or extent of the symptoms/signs are unexpected based on the natural history or bear a strong temporal relationship to the study product as determined by the Investigator). Data on the subject's CLI status of the index limb will be recorded in detail on non-AE CRFs and is not required to be documented as an SAE. Frequently worsening of CLI may lead to hospitalization followed by local or systemic treatment or surgical intervention (minor amputation, surgical revascularization or major amputation). The entries for the above events will be made in the CLI section of the CRF. However, in the case of serious intercurrent illness or systemic complications like septicemia, multi-organ failure, or pneumonia, these events will be captured in the AE or SAE section of the CRF.

8.1.3. Deaths Following Worsening of CLI

CLI-Related Adverse Events or CLI -Related Serious Adverse Events that result in death will be reported. The death will be captured on the SAE CRFs.

CLI-Related Deaths include but are not limited to the following:

- Deaths due to infected ulcers/gangrene that lead to septicemia/organ failure
- Perioperative Deaths following revascularization
- Perioperative Deaths following major amputation
- Worsening of CLI leading to death resulting from complications of Diabetic Ketoacidosis/Renal Failure

8.1.4. Deaths

All deaths will be documented in the CRFs in a specified section. In the event of death, the Investigator will seek permission for an autopsy examination. Information on deaths will be obtained during the Post-18 month follow-up via questionnaire. Hospital discharge reports or death certificates will be requested from the nearest relative.

8.2. Definitions

8.2.1. Treatment-Emergent Adverse Events

The following definition of a **treatment-emergent adverse event** will be used for this study: Any unfavorable and unintended diagnosis, symptom, sign (including an abnormal laboratory finding that is considered to be clinically significant), syndrome or disease which, either occurs during the study, having been absent at baseline, or if present at baseline, appears to have worsened in severity or frequency, whether or not the event is considered related to the study product.

It is the responsibility of the Investigator(s) to perform periodic assessments for adverse events. The Investigators and clinical staff will document all adverse events disclosed by the subject at baseline and during the treatment and follow-up periods. All clinical complaints volunteered by, or elicited from, the subject during the study or from findings on the subject's physical examination will be recorded in the clinical records and on the Adverse Event CRF. If any adverse event occurs, the subject will receive appropriate medical treatment and supervision. All adverse events will be followed until resolution where possible.

For the purpose of this study, index leg specific events that relate to the worsening of the subject's CLI will not be reported as Adverse Events unless applicable. (Please see Section 8.1).

8.2.2. Serious Adverse Event

A **serious adverse event** (21 CFR 312.32) is defined as any adverse event (excluding worsening CLI events if applicable) that suggests a significant hazard, contraindication, side effect or untoward medical occurrence that:

- Results in death,
- Is life-threatening,
- Requires (or prolongs) hospitalization,
- Causes persistent or significant disability/incapacity,
- Results in congenital anomalies or birth defects, or
- Other significant medical conditions which in the judgment of the investigator(s) or Sponsor represent significant hazards.

For the purpose of this study, index leg specific events that relate to the worsening of the subject's CLI will not be reported as Serious Adverse Events unless applicable. (Please see Section 8.1)

Any **serious and immediately life-threatening** adverse event, including death, occurring while the subject is receiving an investigational drug or control agent; within 18 months of the first administration of study product; and throughout the safety follow-up period, irrespective of the Investigator's opinion regarding drug relationship, will be reported by phone to the Sponsor and faxed **immediately**.

All serious adverse events will be reported by contacting the Sponsor/Safety Medical Monitor. The Safety Medical Monitor is available for medical consultation issues related to management of serious adverse events. Contact information regarding the Sponsor/Safety Medical Monitor can be found in the Study Reference Manual provided at the time of the Initiation Monitoring Visit.

